5.6.1.2 Study power

The statistical test planned in the protocol for testing the hypothesis was the one-sided one-sample t-test but the one-sided one-sample Wilcoxon Signed test was finally used due to non-normal distribution of the variables. The margin (δ) selected in the protocol was 0.1 logMAR but the hypothesis was finally also confirmed with a margin of 0.02 logMAR. The software G-Power 3.9.1.2 (Universität Düsseldorf) for an alpha level of 0.05 was used to calculate the power considering the standard deviation obtained in our study.

Table 1. Sample size confirmation

Variables	μ_a	μ_b	Power $\delta = 0.1$	Power $\delta = 0.02$
UDVA	0.06 ± 0.12 0.1 [0.1]	0.03 ± 0.13 0 [-]	0.96	0.12
CDVA	-0.05 ± 0.07 -0.1 [0.1]	0.01 ± 0.11 0 [-]	1	0.99
UIVA	0.07 ± 0.09 0.0 [0.1]	0.12 ± 0.13 0.1 [-]	1	0.99
DCIVA	0.08 ± 0.09 0.1 [0.1]	0.11 ± 0.12 0.1 [-]	1	0.94
UNVA	0.08 ± 0.10 0.1 [0.1]	0.27 ± 0.15 0.2 [-]	1	1
DCNVA	0.05 ± 0.06 0 [0.1]	0.25 ± 0.14 0.2 [-]	1	1

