1 SYNOPSIS

Name of Sponsor: Qvision, Ophthalmology Department, Vithas Virgen del Mar Hospital, [name]	
Name of Finished Product: AT LISA 839MP	
Title of Study: Long-term visual performance and patient reported outcomes with a trifocal intraocular lens	
Principal Investigator: [name]	
Study centre(s): Qvision, Ophthalmology Department, Vithas Virgen del Mar Hospital, [name]	
Studied period (years): 15-9-2020 to 27-11-2020	Phase of development: Post-market
Objectives: The main aims of this study were to evaluate the patient reported outcomes (PROs), safety and efficacy, after 6-year (66 - 78 months) from the binocular implantation of the 839MP. A secondary aim was to evaluate new metrics such as contrast sensitivity defocus curves and light distortion analysis.	
Methodology: Retrospective cross-sectional study with two stages: 
 • Phone call interview: 
First stage included patient reported outcomes of visual function, spectacle independence and satisfaction through questionnaires conducted by a phone call in all the patients implanted in our center with AT LISA 839MP from March 2014 to June 2015 (n=92) which accomplished inclusion / exclusion criteria and were able to be contacted by phone (n=62).
 
The incidence of Nd-YAG capsulotomy was retrospectively evaluated through the revision of the medical history, in patients for which capsulotomy was conducted in our center, or a question, for those treated in another center.
 
 • Study visit: 
Second stage included the consecutive invitation of these phone interviewed patients to a visit in our center for a long-term visual performance assessment up to accomplish the required sample size (n=37).
 
Corrected and uncorrected monocular visual acuities were the primary end-points for testing non-inferiority hypothesis in comparison to 12-month follow-up mean results reported in the literature. Secondary variables of assessment were contrast sensitivity defocus curve and light distortion analysis.
	

Number of patients (planned and analyzed):
92 for PROs planned and 62 analyzed
37 for visual performance planned and analyzed

Inclusion Criteria:

- Phone call interview:
 - Patients of either sex, 45 years of age or older at the time of surgery and less than 80 years of age at the time of the phone call.

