5.5.9 Visual acuity

- Measured in monocular vision with and without the best correction obtained in the subjective refraction.
- Measured in binocular vision without correction.
- Measurements conducted at three distances:
 - Infinity: 4 m with distance vergence correction (+0.25 D)
 - Intermediate: 67 cm
 - Near: 40 cm
- The procedure for measuring visual acuity was carried out with the ETDRS optotype chart (VisionC ETDRS chart, test-eye.com), selecting different sets of letters for each eye and distance in order to avoid a possible bias due to the effect of memorizing letters.
- The procedure for determining the visual acuity threshold was carried out as follows:
 - Read only the first letter from the left and go down.
 - At the first failure, stayed on the previous line and read the whole line.
 - If correct answers were $\geq 3/5$ advanced to the next line.
 - If correct answers were $< 3/5$ read the previous line.
 - Visual acuity was the last with correct answers $\geq 3/5$.

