5.6.1 Hypothesis and sample size calculation

5.6.1.1 Main hypothesis (non-inferiority)

The primary objective was to assess long-term efficacy by measuring monocular visual acuity with and without correction at distance (CDVA and UDVA), intermediate (DCIVA and UIVA) and near (DCNVA and UNVA). The mean monocular visual acuity and the standard deviations taken as reference were obtained from previous literature.¹⁵ Visual acuity was measured on a logMAR scale so that the smaller the variable, the higher the visual acuity.

A contrast of non-inferiority hypotheses with unilateral significance was carried out, rejection of null hypothesis means that non-inferiority was accomplished:

$$H_0 = \mu_a \geq \delta + \mu_b$$

$$H_A = \mu_a < \delta + \mu_b$$

H_0 = Visual acuity at 6 years was higher or equal (poorer) than at 12 months plus a margin δ

H_A = Visual acuity at 6 years was lower (better) than at 12 months plus a margin δ

μ_a = Mean monocular visual acuity obtained after 6 years of follow-up

μ_b = Mean monocular visual acuity reported in a previous clinical study with 12 months of follow-up.¹⁵

δ = 0.1 logMAR or 0.02 logMAR

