5.6.2 Statistical analysis methods

- Normal distributions were tested with the Shapiro-Wilk test
- Wilcoxon-signed rank test one sample was finally selected for testing the hypothesis for median differences because of the non-normal distribution of the variables.
- Correlations were assessed with the Spearman rho or Multiple Linear Regression for multiple correlations and a single dependent variable.
- Descriptive statistics are detailed in the results section as mean ± standard deviation [median (interquartile-range)].
- A survival analysis was performed for the assessment of Nd:YAG rates.
- SPSS version 24 software (SPSS Inc, Chicago, IL, USA) was used for the statistical analysis.

- The Refractive Analysis toolbox for MATLAB (R2019; MathWorks, Natick, MA, USA) was used for conducting the standard plots.³⁰

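### Non-inferiority at 0.02 logMAR is claimed without exception, but the UDVA row of Table 1 does not meet that margin

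*Combined protocol and SAP*

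**What the plan says.** Section 5.6.1.1 sets one non-inferiority hypothesis for six monocular acuities, "at distance (CDVA and UDVA), intermediate (DCIVA and UIVA) and near (DCNVA and UNVA". Lower logMAR is better, and the alternative is "H_A = Visual acuity at 6 years was lower (better) than at 12 months plus a margin δ". The margin is listed there as "δ = 0.1 logMAR or 0.02 logMAR".

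Section 5.6.1.2 discloses that 0.1 was the protocol margin, then states that "the hypothesis was finally also confirmed with a margin of 0.02 logMAR". No acuity is excepted. Table 1 in the same section gives UDVA at 6 years as "0.06 ± 0.12 0.1 [0.1"] (mean ± SD, then median and interquartile range). The 12-month reference has mean 0.03, SD 0.13 and median 0. The printed UDVA power is 0.96 at the 0.1 margin and 0.12 at the 0.02 margin.

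On the test, section 5.6.2 says the "Wilcoxon-signed rank test one sample was finally selected for testing the hypothesis for median differences". The Synopsis gives "37 for visual performance planned and analyzed" as the number of patients, while Appendix B shows acuity measured in both eyes. The number of observations behind Table 1 is not stated.

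**The concern.** A one-sided non-inferiority claim needs the estimate to lie below the limit by more than sampling error. For UDVA at 0.02 the estimate lies above the limit, so no sample size would turn these figures into a confirmation. The power cell raises a second doubt. When the observed effect is on the null side, power toward the alternative, computed from that effect, cannot exceed alpha, yet the table prints 0.12 against an alpha of 0.05.

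UDVA is one of the six acuities under the primary objective, and 0.02 appears beside 0.1 as a margin of the main hypothesis. A reader who relies on the sentence would take uncorrected distance acuity as preserved to within 0.02 logMAR at six years, which the printed data do not show.

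**Working it through.** **Inputs (Table 1 unless noted).** UDVA at 6 years: mean 0.06, SD 0.12, median 0.1. Reference: mean 0.03, median 0. One-sided alpha 0.05 (5.6.1.2). n = 37 is assumed from the Synopsis; n = 74 is also checked because both eyes were measured.

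**1. Reproducing the printed power.** Effect size d = (reference + δ − 6-year mean)/SD. One-sample, one-sided power from the noncentral t distribution, with the Wilcoxon test handled by replacing n with n × 3/π:

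| Cell | d | n = 37 | n = 74 | Printed |
|---|---|---|---|---|
| UDVA, δ = 0.1 | 0.07/0.12 = 0.583 | 0.960 | 0.999 | 0.96 |
| DCIVA, δ = 0.02 | 0.05/0.09 = 0.556 | 0.944 | 0.999 | 0.94 |
| UDVA, δ = 0.02, sign dropped | 0.083 | 0.123 | 0.171 | 0.12 |
| UDVA, δ = 0.02, sign kept | −0.01/0.12 = −0.083 | 0.017 | 0.010 | 0.12 |

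The t-test versions of the last two rows at n = 37 are 0.126 and 0.016. Table 1 is therefore consistent with n = 37 and, in the UDVA cell at 0.02, with an unsigned effect size. With the sign kept, power is at most 0.05, reached only if rounding puts the mean exactly on the limit.

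**2. The UDVA comparison at 0.02.** Limit = 0.03 + 0.02 = 0.05, and 0.06 − 0.05 = +0.01.

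- n = 37: SE = 0.12/√37 = 0.0197; t = 0.01/0.0197 = +0.51; lower-tail p (36 df) = 0.69. Upper one-sided 95% bound for the difference = 0.03 + 1.688 × 0.0197 = 0.063.
- n = 74, eyes treated as independent: t = +0.72, p = 0.76, bound 0.053.

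On medians the direction is the same: 0.1 exceeds 0 + 0.02, and it also exceeds 0.05.

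**3. Rounding.** Let the means lie in 0.055–0.065 and 0.025–0.035, and the SD in 0.115–0.125. The difference is then 0.02 to 0.04.

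- n = 37: p from 0.50 to 0.85, bound from 0.052 to 0.075.
- n = 74: p from 0.50 to 0.93, bound from 0.042 to 0.064.

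Every bound is above 0.02.

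**4. The Wilcoxon test.** Section 5.5.9 scores whole lines ("Visual acuity was the last with correct answers" at or above 3/5), so scores move in steps of 0.1. Assuming n = 37 and values from −0.2 to 0.5, all score distributions matching the printed mean, SD, median and interquartile range were listed: 2,281 to 2,547, depending on the quartile definition. The smallest one-sided Wilcoxon p (normal approximation) is 0.40 against 0.05 and 0.83 against 0.02. With the interquartile condition dropped (3,349 distributions), the minima are 0.40 and 0.63.

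**5. The planned margin and the other acuities.** UDVA against 0.03 + 0.1 = 0.13: t = (0.06 − 0.13)/0.0197 = −3.55, p = 0.0005 at n = 37. The largest Wilcoxon p among the interquartile-matched distributions is 0.009. Upper bounds for the other five at n = 37 are CDVA −0.041, UIVA −0.025, DCIVA −0.005, UNVA −0.162 and DCNVA −0.183. The largest under worst-case rounding is DCIVA: 0.085 − 0.105 + 1.688 × 0.095/√37 = +0.006, still below 0.02.

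**The case against.** The strongest reply is that the weakness is partly visible. Table 1 sits under the sentence, prints 0.06 against 0.03, and shows 0.12 where every other cell is 0.94 or more. The text also says that 0.1 was the protocol margin. This limits how far a careful reader would be misled, but low power suggests an inconclusive test, not an estimate beyond the limit, and neither fits a claim of confirmation.

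Second, the actual Wilcoxon p-values are not in the document, and the p-values and bounds in steps 2 and 3 come from the t-test that was set aside for non-normality. No rule says whether all six acuities must pass, so the sentence might mean the hypothesis as a whole. The first part stands as a caution: the finding is that the printed summaries do not support the claim. However, mean and median both lie on the null side, and no matching score distribution comes near rejection.

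Third, medians cut both ways. If the reference is the median, the planned limit is 0 + 0.1 = 0.1, exactly the 6-year median, and the one-sided Wilcoxon p against 0.1 ranges from 0.004 to 0.113 across matching distributions. This stands as a qualification: the reassurance at 0.1 depends on the reference being the mean, as 5.6.1.1 defines it, while 5.6.2 speaks of medians.

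Fourth, the unsigned effect size is an inference, because the software inputs are not shown. That is correct, and the main point does not depend on it.

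**Conclusion.** The concern holds. The claim of confirmation at 0.02 logMAR is contradicted by the UDVA row of the document's own table: the difference is +0.03 against a margin of 0.02, with p = 0.69 and upper bound 0.063 if n = 37, or 0.76 and 0.053 if n = 74. No rounding or choice between these two n values reverses this. The 0.12 power figure cannot be power toward the stated alternative, which is about 0.016 and at most 0.05.

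The scope is narrow: one of six acuities, at an added margin. UDVA meets the planned 0.1 margin when compared with the reference mean, and the other five appear to meet both margins from their printed means and SDs. It should be fixed because a stated conclusion on a primary acuity is not supported. The planned-margin conclusion is not overturned.

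**What to change.** - In 5.6.1.2, say that all six acuities are assessed against the planned 0.1 margin. Describe 0.02 as an unplanned additional analysis that the printed UDVA figures do not meet and that the other five appear to meet, subject to the Wilcoxon results.
- In 5.6.1.1, label 0.02 as added after the protocol, so that it does not read as an equal alternative margin.
- In Table 1, delete the UDVA 0.12 cell, or replace it with a clearly labelled upper confidence bound and its n (about 0.063 if 37, 0.053 if 74 eyes).
- State the n behind Table 1 and whether the Wilcoxon reference value was the published mean or median, and report the UDVA p-value at both margins.

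The cost is one sentence, one label, one table cell and a short note. No new data are needed. The Wilcoxon results should already exist and only need to be reported.

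### Table 1 computes power at the study's own observed means and SDs, so it does not confirm n=37 for the added 0.02 logMAR margin, where no-change power is only about 0.2 to 0.6

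*Combined protocol and SAP*

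**What the plan says.** The Synopsis gives the size of the visual performance stage as "37 for visual performance planned and analyzed". Section 5.6.1.1 defines the 6-year mean as the one found in this study and compares it with a 12-month published mean. It adds: "The mean monocular visual acuity and the standard deviations taken as reference were obtained from previous literature".

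Section 5.6.1.2 says "The margin (δ) selected in the protocol was 0.1 logMAR" and that the hypothesis was in the end also confirmed at 0.02. A one-sided one-sample t-test was planned, but "the one-sided one-sample Wilcoxon Signed test was finally used due to non-normal distribution of the variables". Power was computed "for an alpha level of 0.05", and the software "was used to calculate the power considering the standard deviation obtained in our study". The results appear under the title "Table 1. Sample size confirmation". In the order UDVA, CDVA, UIVA, DCIVA, UNVA, DCNVA, they are 0.96, 1, 1, 1, 1, 1 at margin 0.1 and 0.12, 0.99, 0.99, 0.94, 1, 1 at margin 0.02.

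No power under an assumed true difference, such as no change, is given for either margin. The planning calculation that led to 37 is not shown.

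**The concern.** A sample size is confirmed by power at an effect fixed independently of the data. Power evaluated at the observed effect is a function of the observed test statistic and n, so it comes out high wherever the result was favourable. In Table 1, five of the six observed means are better than the reference, by 0.03 to 0.20 logMAR, and those five carry 0.94 to 1 at margin 0.02. The sixth, UDVA, is 0.03 worse and carries 0.12.

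The six acuities are the primary endpoints, and Table 1 is the only design support offered for the 0.02 margin. A reader could conclude from it that 37 patients are enough to test a margin one fifth the size of the planned one, or cite it to size a later study.

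**Working it through.** **Inputs.** n=37 (Synopsis); one-sided alpha 0.05 and the signed-rank test (5.6.1.2); means, SDs and margins (Table 1). Assumption: the signed-rank test has efficiency 3/π = 0.955 relative to the t-test, which holds for normal data. Effective n is then 37 × 0.955 = 35.3.

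**Formula.** d = (μ_b + δ − μ_a)/SD, and λ = d × √35.3. Power is the probability that a noncentral t with noncentrality λ and 34.3 degrees of freedom exceeds the one-sided 5% critical value.

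**Step 1: reproduce the plan's figures, with observed means and observed SDs.**
- UDVA, δ = 0.1: d = (0.03 + 0.10 − 0.06)/0.12 = 0.583, λ = 3.47, power 0.960 (printed 0.96; plain t-test 0.967).
- DCIVA, δ = 0.02: d = (0.11 + 0.02 − 0.08)/0.09 = 0.556, λ = 3.30, power 0.944 (printed 0.94; plain t-test 0.953).
- Other cells at 0.02: CDVA 1.000, UIVA 0.998, UNVA 1.000, DCNVA 1.000 (printed 0.99, 0.99, 1, 1). At 0.1, the other five are 1.000 (printed 1).
- UDVA at 0.02 is a separate anomaly. The observed mean 0.06 lies beyond 0.03 + 0.02 = 0.05, so signed power is about 0.02. The printed 0.12 appears (0.123) only if the sign is dropped.

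Two alternatives do not fit DCIVA at 0.02: the literature SD gives 0.80 (t-test), and counting 74 eyes gives 0.999. The t-test and the signed-rank version both fit closely, and both use the observed means.

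**Step 2: power with no true change.** Set μ_a = μ_b, so d = δ/SD. For CDVA at 0.02, the observed SD gives d = 0.02/0.07 = 0.286, λ = 1.70, power 0.51. The literature SD gives d = 0.02/0.11 = 0.182, λ = 1.08, power 0.28.

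| Endpoint | Observed SD | Literature SD | Printed, δ=0.02 | No change, observed SD | No change, literature SD |
|---|---|---|---|---|---|
| UDVA | 0.12 | 0.13 | 0.12 | 0.25 | 0.23 |
| CDVA | 0.07 | 0.11 | 0.99 | 0.51 | 0.28 |
| UIVA | 0.09 | 0.13 | 0.99 | 0.36 | 0.23 |
| DCIVA | 0.09 | 0.12 | 0.94 | 0.36 | 0.25 |
| UNVA | 0.10 | 0.15 | 1 | 0.32 | 0.19 |
| DCNVA | 0.06 | 0.14 | 1 | 0.62 | 0.21 |

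Plain t-test values are within 0.02 of these. With the lower efficiency bound of 0.864, the ranges become 0.24 to 0.58 (observed SDs) and 0.18 to 0.26 (literature SDs).

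**Step 3: the protocol margin.** At δ = 0.1 with no change, the lowest value is UNVA with the literature SD: d = 0.10/0.15 = 0.667, power 0.987. Every other endpoint is higher, with either SD.

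**Step 4: patients needed for 80% power at 0.02 with no change (t-test).** With observed SDs the number runs from 58 (SD 0.06) to 224 (SD 0.12). With literature SDs it runs from 189 (SD 0.11) to 350 (SD 0.15). All exceed 37.

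**The case against.** The authors can fairly say that much is disclosed. Section 5.6.1.2 states that 0.1 was the protocol margin and that the study's own SD was used, so a reader can see that the calculation is retrospective. The table also does not claim adequacy throughout, since it prints 0.12 for UDVA. Post hoc power plays no part in the test or its type I error, and low prior power does not undo a rejected null hypothesis. All of this stands. What is not disclosed is that the observed means were used as the true means; the sentence on power names only the SD.

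Four stronger readings are tempting, and the documents do not support them.
- A reader might infer that power at 0.02 is 0.2 to 0.3 and that the design would usually fail. That holds with the literature SDs only. With the observed SDs, CDVA reaches 0.51 and DCNVA 0.62.
- A reader might see 5.6.1.1 and 5.6.1.2 as contradicting each other on the SD. They do not. The first names the source of the reference values, and nothing there says those SDs drive the power. In a one-sample test against a fixed value, using the SD of the 6-year sample is defensible.
- A reader might conclude that 37 patients were too few. At the planned margin they were not.
- A reader might note that 37 gives 99% t-test power at margin 0.1 with SD 0.15 and take that as the planning basis. That is a match found by back-solving; the documents do not state it.

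**Conclusion.** The point holds as a defect of method and labelling. Table 1 gives observed-effect power, so its 0.94 to 1 at margin 0.02 is not a property of the design. With no true change, power at 0.02 is below 0.8 for all six endpoints under either SD, between about 0.2 and 0.6. The sample size of 37 remains adequate for the planned 0.1 margin.

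The result rests on these assumptions: 37 as the number of independent observations, which is the count that reproduces the table; the reference mean treated as fixed, as in the plan; and signed-rank efficiency for normal data, although the plan describes the data as non-normal. Table inputs are rounded to 0.01, which alone moves observed-effect power for DCIVA at 0.02 over about 0.81 to 0.99. The match to the printed cells is therefore close but not exact proof of the software settings. The use of observed means is inferred from the definition in 5.6.1.1 together with that match.

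**What to change.** 1. Replace both power columns with power at a 6-year mean equal to the reference mean, and name the SD source, preferably showing both: at least 0.987 at margin 0.1, and the two no-change columns tabulated above at 0.02.
2. Do not present any figure computed at observed means as confirming the sample size. If it is kept at all, label it as observed-effect power.
3. State that n=37 is adequate for 0.1 logMAR, and that 0.02 is a post hoc margin for which the design has power of only about 0.2 to 0.6.

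The cost is a rerun of the power calculations for six endpoints and edits to one table and its accompanying text. No new data are needed and the non-inferiority tests are unchanged. The stated power at 0.02 becomes much less favourable, while the 0.1 margin gains a valid justification that the table does not now give it.

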5.6.2 Statistical analysis methods

- Normal distributions were tested with the Shapiro-Wilk test
- Wilcoxon-signed rank test one sample was finally selected for testing the hypothesis for median differences because of the non-normal distribution of the variables.
- Correlations were assessed with the Spearman rho or Multiple Linear Regression for multiple correlations and a single dependent variable.
- Descriptive statistics are detailed in the results section as mean ± standard deviation [median (interquartile-range)].
- A survival analysis was performed for the assessment of Nd:YAG rates.
- SPSS version 24 software (SPSS Inc, Chicago, IL, USA) was used for the statistical analysis.

- The Refractive Analysis toolbox for MATLAB (R2019; MathWorks, Natick, MA, USA) was used for conducting the standard plots.³⁰

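### Non-inferiority is stated on means but tested with a signed-rank test described as a test of medians; the hypothesis, test value and margin were not restated, and symmetry is not reported

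*Combined protocol and SAP*

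**What the plan says.** Section 5.6.1.1 defines the study parameter as "Mean monocular visual acuity obtained after 6 years of follow-up" and the reference parameter as a published 12-month mean: "The mean monocular visual acuity and the standard deviations taken as reference were obtained from previous literature". The null hypothesis is that the six-year mean is at or above the reference mean plus a margin. The Synopsis agrees, describing the comparison as made "in comparison to 12-month follow-up mean results reported in the literature".

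Section 5.6.1.2 says: "The statistical test planned in the protocol for testing the hypothesis was the one-sided one-sample t-test". It adds that a one-sample signed-rank test was used in the end because the variables were not normal. It keeps the planned margin of 0.1 logMAR and adds a second: "the hypothesis was finally also confirmed with a margin of 0.02 logMAR".

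Section 5.6.2 reports the only distribution check, "Normal distributions were tested with the Shapiro-Wilk test", and then the replacement: "Wilcoxon-signed rank test one sample was finally selected for testing the hypothesis for median differences because of the non-normal distribution of the variables".

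Table 1 prints a median beside each mean, for the study and for the reference, under column headings still defined as means. No section says which reference figure was entered as the test value.

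**The concern.** The signed-rank test targets the pseudo-median. It is a valid test of the stated mean hypothesis in general only when the distribution is symmetric about the limit. Without symmetry its p-value answers a different question: it passes too often under right skew and too rarely under left skew. A test of normality does not settle symmetry, and symmetry is not reported.

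The unstated test value adds a second ambiguity. For UDVA at margin 0.1 the limit is 0.03 + 0.1 = 0.13 if built on the printed reference mean, but 0 + 0.1 = 0.10 if built on the printed reference median. The study median is itself 0.1. These are the primary endpoints, so a reader should be able to tell which quantity was compared with which limit.

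**Working it through.** **Inputs.** Table 1 (Section 5.6.1.2) gives study mean ± SD and reference mean. UDVA: 0.06 ± 0.12 against 0.03. CDVA: -0.05 ± 0.07 against 0.01. UIVA: 0.07 ± 0.09 against 0.12. DCIVA: 0.08 ± 0.09 against 0.11. UNVA: 0.08 ± 0.10 against 0.27. DCNVA: 0.05 ± 0.06 against 0.25. Alpha is 0.05, one-sided. The number of values, 37, comes from the Synopsis; Table 1 does not state it.

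**1. Reproduce the plan's power.** I used one-sample non-central t power with effect (limit - mean)/SD and n multiplied by 3/π, the signed-rank efficiency for normal data.

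- UDVA, limit 0.13: effect 0.07/0.12, n = 37, power 0.960. The plan gives 0.96.
- n = 74 (both eyes): 0.999, which does not fit.
- Limit 0.10, n = 37: effect 0.04/0.12, power 0.62, which does not fit.
- UDVA at margin 0.02: the plan's 0.12 reproduces (0.123) only if the sign of the effect is dropped. With the sign kept, power is 0.017.

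The power table therefore rests on means and 37 values, although the test is described as one of medians.

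**2. The planned t-test.** t = (mean - reference - δ)/(SD/√37), df 36. Upper bound = mean - reference + 1.688 × SD/√37. For UDVA, SD/√37 = 0.0197. Reference means are taken as fixed.

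| Endpoint | Mean difference | One-sided 95% upper bound | p at 0.1 | p at 0.02 |
|---|---|---|---|---|
| UDVA | 0.03 | 0.063 | 0.0005 | 0.69 |
| CDVA | -0.06 | -0.041 | < 1e-10 | ≤ 0.0009 |
| UIVA | -0.05 | -0.025 | < 1e-10 | ≤ 0.0009 |
| DCIVA | -0.03 | -0.005 | < 1e-10 | 0.0009 |
| UNVA | -0.19 | -0.162 | < 1e-10 | ≤ 0.0009 |
| DCNVA | -0.20 | -0.183 | < 1e-10 | ≤ 0.0009 |

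Allowing for rounding in Table 1, UDVA p is at most 0.003 at 0.1 and lies between 0.50 and 0.85 at 0.02. If the reference means also carry sampling error (Welch test, printed reference SDs, assumed reference n of 20, 40 or 100), the UDVA bound is 0.089, 0.077 or 0.069. Its p at 0.1 is then 0.027, 0.008 or 0.002, and all six endpoints still pass at 0.1.

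**3. Type I error for the mean.** Simulated acuity was gamma or mirrored gamma, rounded to 0.1 logMAR (assumed step), SD about 0.12, n = 37, true mean at the limit 0.13, nominal 0.05, with 20,000 samples per shape.

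| Skewness | Signed-rank | t-test |
|---|---|---|
| 0 | 0.035 | 0.051 |
| 0.93 | 0.097 | 0.066 |
| 1.28 | 0.136 | 0.079 |
| -0.91 | 0.010 | 0.036 |
| -1.25 | 0.006 | 0.032 |

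At limit 0.05 the signed-rank values are 0.052 with no skew, 0.115 and 0.152 at right skewness 0.92 and 1.23, and 0.015 and 0.012 at left skewness 0.94 and 1.24.

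**4. What Shapiro-Wilk can show here.** Section 5.5.9 scores acuity by whole line. If a symmetric normal variable is rounded to 0.1 logMAR, the test rejects at n = 37 in about 0.90 of samples (SD 0.12), 0.99 (SD 0.10) and 1.00 (SD 0.09 or less). A significant result is expected from the scoring alone and says nothing about skew.

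**5. UDVA data sets that match Table 1.** I generated sets of 37 values on a 0.1 grid from -0.3 to 0.6 that match the printed mean, SD, median and IQR within rounding. This gave 1,128 distinct sets with skewness from -2.3 to 2.8.

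| Limit | Signed-rank p | t-test p |
|---|---|---|
| 0.13 (reference mean + 0.1) | 2e-7 to 0.0083 | 0.0003 to 0.0014 |
| 0.10 (reference median + 0.1) | 0.0007 to 0.113 | 0.015 to 0.045 |
| 0.05 (reference mean + 0.02) | 0.40 to 0.99 | 0.63 to 0.78 |

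At 0.13 both tests pass in every set. At 0.05 neither passes in any. At 0.10 the signed-rank outcome depends on the set, because 11 to 27 of the 37 values tie with the limit and drop out.

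**The case against.** The strongest reply is that nothing changes at the protocol margin. The switch and its reason are disclosed in two sections. The hypothesis section fixes the limit as reference mean plus margin, and the UDVA power fits 0.13. On that reading 0.10 was never a limit, and most matching UDVA data sets would pass there too: in a wider enumeration of 4,864 sets, about 9% exceeded p = 0.05 (a count of sets, not a probability). The type I error figures rest on assumed shapes and a true mean at the limit, far from the observed 0.06. The UDVA mean lies below its median, which hints, if anything, at left skew, where the signed-rank test is conservative. The t-test is not exact either, at 0.07 to 0.08 under right skew. Finally, the 0.02 claim is a separate error.

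Much of this stands. No result at 0.1 is overturned on the mean limit, the skew figures show direction and scale only, and the exact bounds in step 5 depend on the quartile rule (the wider enumeration gave a maximum of 0.0094 at 0.13). But disclosing a change of test does not align it with the hypothesis. The power calculation shows which limit the power used, not which value was entered in the test. The median reading comes from the plan's own wording and printed medians. The t-test stays closer to its nominal level in every skewed case. The 0.02 statement is indeed separate from the change of test, but it sits in the same paragraph and contradicts Table 1.

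**Conclusion.** The concern holds. The stated hypothesis is on means, the test used is not in general a test of means, and the plan gives neither the test value nor a restated hypothesis and margin. At the protocol margin of 0.1 this is a fault of target and reporting: all six endpoints pass the planned t-test on the stated limit, and UDVA, the weakest, has an upper bound of 0.063. If the printed reference median had been used instead, the UDVA outcome could not be determined from Table 1.

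Independently of the change of test, UDVA does not meet the 0.02 margin on the stated hypothesis, so the confirmation claimed there is wrong for that endpoint.

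These conclusions assume 37 independent values. The t-test figures treat the reference means as fixed unless noted, and the simulations and matching data sets assume scoring in 0.1 logMAR steps. The direction of any skew in the patient data is unknown.

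**What to change.** - For all six endpoints, make the planned one-sample t-test against reference mean plus margin the primary analysis, whatever Shapiro-Wilk shows. Report the mean difference with its one-sided 95% upper bound, and say that the published means are treated as fixed constants. A bootstrap bound is an optional check for skew.
- Report the signed-rank test as a sensitivity analysis, naming the pseudo-median as its target and giving the test value used.
- If the signed-rank test is kept as primary instead, restate the hypothesis, reference value and margin for it and label the change as post hoc.
- Correct Section 5.6.1.2: on the stated mean hypothesis UDVA meets the 0.1 margin but not 0.02.

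The cost is wording in the SAP and report plus six re-runs on existing data, with no new measurements. No conclusion at 0.1 is lost on the stated mean limit; the one less favourable statement is UDVA at 0.02.
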